7.6 Multiple Comparisons/Multiplicity

The following stepwise process will be conducted for testing the secondary efficacy endpoints in order to control for multiplicity. These tests will be performed for only the intent-to-treat (ITT) population. The testing process will terminate whenever a statistical test for a step is not significant. All subsequent tests for the remaining steps will be considered not significant. The order of testing is percent change in inflammatory lesion count from Baseline to Week 12, percent change in non-inflammatory lesion count from Baseline to Week 12 and the proportion of subjects who are dichotomized to success (minimum 2-grade improvement from Baseline).

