A total of 420 adult subjects were randomized to active and vehicle in a 2:2:2:1:1 fashion. Study treatments continued for 12 weeks. Subjects returned to the study clinic at Weeks 1, 2 (phone call only), 4, 8 and 12 (study exit).

The results of the study showed that all three Olumacostat Glasaretil Gel treatment groups demonstrated statistically significantly greater reductions in the absolute change in inflammatory lesion counts from baseline to Week 12 than the combined vehicle group. The LS mean changes in inflammatory lesion counts were -14.6 and -14.5, and -15.0 for the Olumacostat Glasaretil Gel, 4.0% QD, 7.5% QD, and 7.5% BID groups, respectively, compared with -10.7 for the combined vehicle QD group (P = 0.011, P = 0.014, and P = 0.011 respectively). All 3 Olumacostat Glasaretil Gel treatment groups showed statistically significantly greater reductions in the absolute change in noninflammatory lesion counts from baseline to Week 12 than the combined vehicle group. The LS mean changes in noninflammatory lesion counts at Week 12 were -15.3, -13.4, and -17.5 for the DRM01B Olumacostat Glasaretil Gel 4.0% QD, 7.5% QD, and 7.5% BID groups, respectively, compared with -9.3 for the combined vehicle group (P = 0.004, P = 0.050, and P < 0.011 respectively).

The Olumacostat Glasaretil Gel 4.0% QD and 7.5% BID groups each had a statistically significantly greater proportion of subjects achieve a minimum 2-grade improvement (reduction) in IGA score from baseline at Week 12 compared with the combined vehicle group. The percent of subjects achieving this endpoint was 21.6% in the Olumacostat Glasaretil Gel 4.0% QD and 25.9% of subjects in the Olumacostat Glasaretil Gel 7.5% BID group (compared with 9.8% in the combined vehicle QD group (P = 0.024 and P = 0.004, respectively).

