5.3.1 Inclusion Criteria

Subjects must meet all of the following criteria to be eligible for study participation:

- 1. Signed informed consent and, for subjects under legal adult age, signed assent
- 2. Age ≥ 9 years
- 3. Willing to comply with the protocol. Subjects under legal adult age will be assessed by the investigator as to their ability to comply with the protocol
- 4. Male or non-pregnant (negative serum pregnancy test at screening for female subjects of child-bearing potential), non-lactating females
- 5. In the case of females of childbearing potential), are using an acceptable form of birth control (Section 5.3.4)
- 6. In the case of females of childbearing potential, have a negative urine pregnancy test at Baseline/Day 1
- 7. Clinical diagnosis of facial acne vulgaris defined as:
 - At least 20 inflammatory lesions, and
 - At least 20 non-inflammatory lesions, and
 - Investigator Global Assessment of 3 or greater
- 8. Willing to refrain from using any treatments for acne vulgaris, other than the investigational product, including topical or systemic antibiotics.

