11.4 Secondary Efficacy

The percent change from baseline to Week 12 in inflammatory and non-inflammatory lesion counts will be analyzed using the same ANCOVA method described for the primary endpoint.

The proportion of subjects who are dichotomized to success (minimum 2-grade improvement from baseline) at Week 12 will be analyzed using the same logistic analysis method described for the primary endpoint.

The following stepwise process will be conducted for testing the secondary efficacy endpoints in order to control for multiplicity. These tests will be performed for only the ITT population. The testing process will terminate whenever a statistical test for a step is not significant. All subsequent tests for the remaining steps will be considered not significant. The order of testing is percent change in inflammatory lesion count from baseline to Week 12, percent change in non-inflammatory lesion count from baseline to Week 12, and the proportion of subjects who are dichotomized to success (minimum 2-grade improvement from baseline).

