11.14 Sample Size Determination

The sample size for this study was based on estimates from the DRM01B-ACN02 study observed Week 12 results. Estimates were combined for all three active treatment groups as well for the two vehicle groups. All power calculations were performed with nQuery Advisor Version 7.0 for a two-sided test at alpha = 0.05.

For inflammatory lesion change a sample size of 300 Olumacostat Glasaretil Gel and 150 Olumacostat Glasaretil Gel Vehicle subjects has at least 95% power to detect a statistically significant difference with a significance level of 0.05 using the estimated absolute change from baseline in treatment means of -15.21 and -9.7 for Olumacostat Glasaretil Gel versus its vehicle, respectively, with a standard deviation of 11.00.

For non-inflammatory lesion change a sample size of 450 Olumacostat Glasaretil Gel and 225 Olumacostat Glasaretil Gel Vehicle subjects has 95% power to detect a statistically significant difference with a significance level of 0.05 using the estimated absolute change from baseline in treatment means of -14.73 and -9.70 for Olumacostat Glasaretil Gel versus its vehicle, respectively, with a standard deviation of 16.72.

The success rate for dichotomized IGA is estimated to be 20.5% in the 5.0% BID subjects and 9.6% in vehicle subjects. A sample size of 444 Olumacostat Glasaretil Gel and 222 Olumacostat Glasaretil Gel Vehicle will have 95% power to detect a statistically significant difference in proportions of successes. These calculations were performed with nQuery Advisor Version 7.0 for a two-sided continuity corrected chi-square test at alpha = 0.05.

To allow for a slight loss in power due to dropouts and withdrawals as well as to accommodate sufficient power in all three co-primary variables, a sample of 700 subjects randomized to 2 to 1 for Olumacostat Glasaretil Gel (n=467) and vehicle (n=233), respectively, will be enrolled in the trial.

12 STUDY ADMINISTRATION

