4.2 Determination of Sample Size

The sample size for this study was based on estimates from the DRM01B-ACN02 study observed Week 12 results. Estimates were combined for all three active treatment groups as well as for the two vehicle groups. All power calculations were performed with nQuery Advisor Version 7.0 for a two-sided test at $\alpha = 0.05$.

For inflammatory lesion change a sample size of 300 Olumacostat Glasaretil Gel and 150 Olumacostat Glasaretil Gel, Vehicle subjects has at least 95% power to detect a statistically significant difference with a significance level of 0.05 using the estimated absolute change from Baseline in treatment means of -15.21 and -9.7 for Olumacostat Glasaretil Gel versus its vehicle, respectively, with a standard deviation (SD) of 11.00.

For non-inflammatory lesion change a sample size of 450 Olumacostat Glasaretil Gel and 225 Olumacostat Glasaretil Gel, Vehicle subjects has 95% power to detect a statistically significant difference with a significance level of 0.05 using the estimated absolute change from Baseline in treatment means of -14.73 and -9.70 for Olumacostat Glasaretil Gel versus its vehicle, respectively, with a SD of 16.72.

The success rate for dichotomized IGA is estimated to be 20.5% in the Olumacostat Glasaretil Gel subjects and 9.6% in vehicle subjects. A sample size of 444 Olumacostat Glasaretil Gel and 222 Olumacostat Glasaretil Gel, Vehicle will have 95% power to detect a statistically significant difference in proportions of successes. These calculations were performed with nQuery Advisor Version 7.0 for a two-sided continuity corrected chi-square test at $\alpha = 0.05$.

To allow for a slight loss in power due to dropouts and withdrawals as well as to accommodate sufficient power in all three co-primary variables, a sample of 700 subjects randomized to 2 to 1 for Olumacostat Glasaretil Gel (n=467) and vehicle (n=233), respectively, will be enrolled in the trial.

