7.7 Examination of Subgroups

Subset analyses will be conducted for the ITT population for subgroups based on the following:

- Baseline IGA;
 - Categorized as Baseline IGA = 3 (Moderate) and Baseline IGA = 4 (Severe); due to the inclusion criteria requiring subjects to have either a 3 or 4 IGA score at study entry other IGA response categories will not be presented;
- Gender;
- Age:
 - Dichotomized as less than the median age of ITT subjects and greater than or equal to the median age of ITT subjects;
 - Categorized as less than 18, 18 to less than the median age of ITT subjects and greater than or equal to the median age of ITT subjects; If the median age of ITT subjects is less than 18 then the subgroup will be <18 and >= 18
- Ethnicity;
- Race:
 - Categorized as White and Non-White; subjects indicating more than one race category which includes both white and a non-white race will be summarized under the Non-White subgroup.

Subset analyses will be conducted on the variables absolute change from Baseline in inflammatory lesions and non-inflammatory lesions at Week 12 as well as the dichotomized IGA score at Week 12. These analyses will contain descriptive statistics only.

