7.9.7.2 Secondary Efficacy Analyses

The percent change from Baseline to Week 12 in inflammatory and non-inflammatory lesion counts will be analyzed using the same ANCOVA method described for the primary endpoint.

The proportion of subjects who are dichotomized to success (minimum 2-grade improvement from Baseline) at Week 12 will be analyzed using the same logistic analysis method described for the primary endpoint. A stepwise process will be conducted for testing the secondary efficacy endpoints in order to control for multiplicity, refer to Section 7.6 for details.

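### The secondary test sequence is not conditional on the three co-primaries, so a secondary can be declared significant after a co-primary has failed; the added error is modest

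*SAP*

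**What the plan says.** SAP 7.6 opens with "The following stepwise process will be conducted for testing the secondary efficacy endpoints in order to control for multiplicity". The order is percent change in inflammatory lesions, then percent change in non-inflammatory lesions, then improvement of at least 2 IGA grades, all in the ITT population. Protocol 11.4 has the same procedure and gives one stopping rule: "The testing process will terminate whenever a statistical test for a step is not significant". The steps it refers to are the secondaries.

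SAP 7.9.7.2 adds only a pointer: "A stepwise process will be conducted for testing the secondary efficacy endpoints in order to control for multiplicity, refer to Section 7.6 for details". SAP 7.9.7.1 sets out the primary models without linking their results to the secondaries. SAP 7.1 sets 0.05 two-sided per test, and SAP Section 5 lists no relevant change.

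The status of the primaries appears in the sample-size text, where 700 subjects are chosen partly "as well as to accommodate sufficient power in all three co-primary variables". Each of the three is sized at an unsplit 0.05.

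**The concern.** A fixed sequence protects the claims inside it. Here the sequence has its own 0.05, separate from the primaries, and it starts whether or not they succeed. If the IGA co-primary fails, the text still sends the analyst through all three secondaries. The last of these is a looser form of the endpoint that failed. Any result would carry the label of a procedure that controls multiplicity.

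Two things are at stake. One is the chance of a false claim across primary and secondary endpoints together. The other is the status of a positive secondary after a co-primary miss: the plan does not say whether it is a formal claim or a nominal result, so that would be settled after the data are seen.

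**Working it through.** **1. The plan's own figures.** The IGA inputs are in SAP 4.2: "The success rate for dichotomized IGA is estimated to be 20.5% in the Olumacostat Glasaretil Gel subjects and 9.6% in vehicle subjects". At 2:1, the mean rate is (2 × 0.205 + 0.096)/3 = 0.1687. The uncorrected vehicle n is [1.96·√(1.5 × 0.1687 × 0.8313) + 1.645·√(0.205 × 0.795/2 + 0.096 × 0.904)]² / 0.109² = 208.4. The continuity correction multiplies this by ¼[1 + √(1 + 6/(2 × 208.4 × 0.109))]², giving 222 vehicle and 444 active, as stated. The lesion calculations also hold: 95.8% power for non-inflammatory at 450/225 and 99.9% for inflammatory at 300/150. The plan gives no error figure across the two families.

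**2. Planned effects at 467:233.** Noncentrality = difference / (SD·√(1/467 + 1/233)), and the root is 0.0802.
- Inflammatory: 5.51/(11.00 × 0.0802) = 6.25.
- Non-inflammatory: 5.03/(16.72 × 0.0802) = 3.75.
- IGA: 3.55 (Wald log odds ratio) to 3.83 (equivalent to 96.9% power).

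**3. How the two IGA endpoints relate.** Entry needs "Investigator Global Assessment of 3 or greater", and SAP 7.7 describes the criteria as "requiring subjects to have either a 3 or 4 IGA score at study entry". From grade 3, a 2-grade improvement always ends at 0 or 1, so the endpoints coincide. They differ only for subjects who go from grade 4 to grade 2. The success events are nested, with correlation √[p1(1−p2)/(p2(1−p1))], where p1 is the stricter rate and p2 the looser.

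The share of grade 4 subjects ending at grade 2 is not given, so this correlation cannot be fixed from the documents. Protocol 1.2 gives 2-grade rates of 21.6% and 25.9% in two active arms, "compared with 9.8% in the combined vehicle QD group". Pairing these with the rates in SAP 4.2 gives 0.99, 0.97 and 0.86. However, SAP 4.2 does not say which IGA definition produced 20.5% and 9.6%. With three equal active arms, a pooled 20.5% leaves 3 × 20.5 − 21.6 − 25.9 = 14.0% for the third arm. That is compatible with 20.5% being the pooled 2-grade rate, in which case the pairing compares an endpoint with itself. I therefore use 0.99 down to 0.7 as an assumption.

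**4. Error with no IGA effect and planned lesion effects.** A false IGA claim means either that all three co-primaries are significant, or that the 2-grade step is reached and significant. If the lesion tests are certain to reject, the error favouring active is 0.025 + 0.025 − P(both statistics > 1.96). The simulated columns use six correlated normal statistics. Assumptions not in the documents: cross-endpoint correlation 0.3–0.5, absolute–percent correlation 0.85, and percent-change noncentrality 0.7–1.0 times that of absolute change.

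| IGA–IGA correlation | Closed form, favouring active | Simulated, favouring active | Simulated, two-sided |
|---|---|---|---|
| 0.99 | 2.83% | 2.8% | 4.85–5.4% |
| 0.95 | 3.23% | 3.1–3.2% | 5.4–6.1% |
| 0.86 | 3.69% | 3.6–3.7% | 6.0–7.0% |
| 0.70 | 4.17% | about 4.1% | 6.6–7.8% |
| Sequence conditional on co-primaries | 2.5% | 2.5% | 4.4–4.7% |

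**5. Other configurations.**
- No effect on any endpoint: about 5.0–5.1% two-sided, so negligible excess.
- Non-inflammatory co-primary and its percent-change secondary both null: about 3.7% favouring active at correlation 0.85, so the same order.
- IGA co-primary and inflammatory percent change both null: about 9.0% two-sided. This needs a real effect on the absolute inflammatory count and none on the percent change of that count, which is hard to credit.
- General limit for two families at 0.05 each: 0.10 two-sided.

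**6. How often the gap comes into play.** At planned effects and full enrolment, roughly 6–9% of trials miss a co-primary, and the first secondary is significant in 94–100% of those. If IGA has no effect and the lesion effects are as planned, a secondary is declared after a co-primary miss in about 95% of trials. The figure is about 97% if only results favouring active count as success.

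**The case against.** The best defence is that the plan promises only what it delivers. SAP 7.6 speaks of control for the secondary endpoints, and a fixed sequence gives that. No passage claims control across both families, so the plan does not contradict itself. The co-primary results would be reported alongside, so a failure could not be hidden. The secondaries largely restate the primaries, which keeps the excess small. The all-three requirement is already implied by the term co-primary and by sizing each endpoint at an unsplit 0.05.

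All of this stands, and it limits the point. It does not answer the omission: knowing that all three must succeed for the primary claim does not say what becomes of the secondaries when one fails.

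A reader might infer more than the documents support:
- **That this trial's error is 10%.** That is the general limit. The illustrated IGA case is well below it.
- **That a significant lesion secondary after an IGA miss is a false positive.** At planned effects the lesion effects are real, so the 94–100% in step 6 concerns the status of a claim and is not an error rate.
- **That success on any one primary would suffice.** The sample-size wording points the other way.
- **That the Phase 2 rates cap the error at 3.7% (7.0% two-sided).** They do not, because the definition behind 20.5% and 9.6% is not stated.

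**Conclusion.** The concern holds in a limited form. Error is controlled among the three secondaries, but the sequence is not conditional on the co-primaries, and the text as written allows a secondary to be declared significant after a co-primary has failed. That omission is certain from the wording.

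The size is illustrative. With planned lesion effects and no IGA effect, the excess favouring active is about 0.3 to 1.6 percentage points (2.8–4.1% against 2.5%). It rests on the assumed correlations and percent-change factor, full enrolment, and each single test holding its nominal level; the data-driven choice between ranked and unranked models was not examined. This is a cheap improvement and does not threaten the primary conclusion.

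**What to change.** Add to SAP 7.6: *The secondary sequence is tested only if all three co-primary ITT tests are significant at two-sided 0.05 in favour of Olumacostat Glasaretil Gel, 5.0%; otherwise secondary p-values are nominal.* The direction matters: without it, a co-primary significantly favouring vehicle would open the sequence.

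Record the departure from Protocol 11.4 in SAP Section 5, which already lists such changes. Align Protocol 11.4 if the protocol is amended for another reason; an amendment for this alone would need the ethics approval described in Protocol 12.1. The sentence should be in place before unblinding, when Protocol 11.1 requires the SAP to be final.

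No alpha or sample size is spent, and the primary tests and secondary order are unchanged. The downside is losing formal secondary claims when a co-primary is missed: roughly 6–9% of trials at planned effects and full enrolment, and somewhat more with dropout. For example, an assumed 10% loss lowers power from 96.3% to 94.4% for non-inflammatory lesions and from 96.9% to 95.1% for IGA (no continuity correction).

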7.7 Examination of Subgroups

Subset analyses will be conducted for the ITT population for subgroups based on the following:

- Baseline IGA;
 - Categorized as Baseline IGA = 3 (Moderate) and Baseline IGA = 4 (Severe); due to the inclusion criteria requiring subjects to have either a 3 or 4 IGA score at study entry other IGA response categories will not be presented;
- Gender;
- Age:
 - Dichotomized as less than the median age of ITT subjects and greater than or equal to the median age of ITT subjects;
 - Categorized as less than 18, 18 to less than the median age of ITT subjects and greater than or equal to the median age of ITT subjects; If the median age of ITT subjects is less than 18 then the subgroup will be <18 and >= 18
- Ethnicity;
- Race:
 - Categorized as White and Non-White; subjects indicating more than one race category which includes both white and a non-white race will be summarized under the Non-White subgroup.

Subset analyses will be conducted on the variables absolute change from Baseline in inflammatory lesions and non-inflammatory lesions at Week 12 as well as the dichotomized IGA score at Week 12. These analyses will contain descriptive statistics only.

7.8 Analysis Populations

7.8.1 Randomized Population

All subjects who are randomized to study treatment will be included in the randomized population and will be analyzed according to the treatment group they were randomized.

7.8.2 Intent-to-Treat (ITT) Population

All subjects in the randomized population who are dispensed study drug will be included in the ITT population and will be analyzed according to the treatment group they were randomized. All efficacy analyses will be presented using the ITT population.

7.8.3 Safety Population

All subjects in the randomized population who receive at least one confirmed dose of study drug and have at least one post-baseline safety assessment will be included in the safety population and will be analyzed according to the treatment they received. All safety analyses will be performed using the safety population.

7.8.4 Per-Protocol (PP) Population

All subjects in the safety population who complete the Week 12 evaluation without any significant protocol violations will be included in the PP population and analyzed according to the treatment group they received. The PP population will include subjects in the safety population who do not meet any of the following criteria:

- Violated the inclusion/exclusion criteria;
- Have taken any interfering concomitant medication;
- Did not attend the Week 12 visit;
- Have missed both the Week 4 and Week 8 study visits;
- Have not been compliant with the dosing regimen (i.e. subjects must apply 80-120% of the expected applications of study medication during participation in the study);
- Out of visit window at the Week 12 visit by ± 5 days.

Subjects that discontinue treatment or from the study due to an AE related to study treatment or documented lack of treatment effect will be included in the PP population. Prior to breaking the blind, other additional criteria may be added to the list to accommodate for unforeseen events that occurred during the conduct of the trial that result in noteworthy study protocol violations.

All efficacy analyses will be performed on the PP population.

7.9 Statistical Analysis

All analyses will be performed by QST. All summary tables and data listings will be prepared utilizing SAS® software. The standard operating procedures of QST will be followed in the creation and quality control of all data displays and analyses.

All data collected at scheduled time points will be summarized, regardless of treatment with study drug. Post-treatment assessments for subjects who discontinue treatment but continued to be followed in the study will be included in summaries.

7.9.1 Baseline Definition

Baseline is defined as the last non-missing assessment prior to the first dose of study drug.

7.9.2 Visit Windowing

Data will be summarized based on nominal visit indications with the exception of data captured at early termination and unscheduled visits. Data from early termination and unscheduled visits will be summarized based on mapped visit values. The analysis windows for early termination and unscheduled visits are presented in the following table.

Analysis Windows for Efficacy and Safety Assessments

Scheduled Visit	Target Study Day	Window (Days)
Week 1	8	5 to 18
Week 4	29	19 to 42
Week 8	57	43 to 70
Week 12	85	71 to 98

Data collected at early termination and unscheduled visits prior to study day 5 will not be analyzed, with the exception of those identified as baseline values. Data collected at early termination and unscheduled visits after study day 98 will not be included in analyses.

The definition for the study day included in each study window is defined as below:

$$\text{Study Day Prior to Day 1} = \text{Visit Date} - \text{Day 1 Date}$$

$$\text{Study Day On or After Day 1} = \text{Visit Date} - \text{Day 1 Date} + 1.$$

If an assessment's mapped visit is a visit at which the subject has data from a scheduled visit present, or if no analyses are planned for the assessment at the mapped visit, the data collected at the early termination or unscheduled visit will not be included in analyses.

In the event of multiple values from unscheduled or early termination assessments within an analysis window, the value closest to the scheduled visit target study day will be used for

analyses. If two values tie as closest to the time point (for example, one value is before and the other value is after the time point), then the later value will be selected.

Data collected at all visits will be included in the data listings with visit presented as reported by the site.

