7.9.8.3 Clinical Laboratory Evaluations

Laboratory test results will be summarized descriptively at Baseline and Week 12. Additionally, shifts from Baseline to Week 12 in laboratory test results based on normal ranges will be summarized with descriptive statistics. Individual laboratory test results will be presented in a by-subject listing.

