7.9.8.5 Other Observations Related to Safety

7.9.8.5.1 ECG Measurements

Descriptive statistics by treatment group and visit will be provided for the following ECG parameters: heart rate (HR), PR duration, RR duration, QRS duration, QT duration, QT interval corrected for heart rate using Bazett's formula (QTcB) and QT interval corrected for heart rate using Fridericia's formula (QTcF). Change from Baseline in ECG abnormalities will be summarized using shift tables at the Week 12 visit. Shift tables will be based on the following categories:

- PR Interval: < 100 msec, 100 – 220 msec and > 220 msec;
- QRS Interval: < 50 msec, 50 – 110 msec and > 110 msec;
- QTcF Interval: < 450 msec, 450 – 500 msec and > 500 msec.

The following treatment-emergent ECG abnormalities will be summarized for subjects in the safety population with at least one post-application ECG:

- PR Interval
 - > 220 msec;
 - > 220 msec and Change from Baseline > 25%;
- QRS Interval

- > 110 msec;
- > 110 msec and Change from Baseline > 25%;
- QTcF Interval
 - > 450 – 480 msec;
 - > 480 – 500 msec;
 - > 500 msec;
 - Change from Baseline > 30 - 60 msec;
 - Change from Baseline > 60 msec;
 - > 450 - 480 msec and Change from Baseline > 30 - 60 msec;
 - > 450 - 480 msec and Change from Baseline > 60 msec;
 - > 480 - 500 msec and Change from Baseline > 30 - 60 msec;
 - > 480 - 500 msec and Change from Baseline > 60 msec;
 - > 500 msec and Change from Baseline > 30 - 60 msec;
 - > 500 msec and Change from Baseline > 60 msec.

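### Early-termination labs and ECGs taken before Day 71 are left out of the Week 12 lab summary, the lab shift table and the ECG shift table

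*SAP*

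**What the plan says.** Protocol 8.7 and Appendix 1 place the only scheduled post-dose safety labs and 12-lead ECG at one visit, which is Week 12 for completers and the ET visit for those who leave early.

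SAP 7.9.2 treats ET and unscheduled data differently from scheduled visits: "Data from early termination and unscheduled visits will be summarized based on mapped visit values". The mapping is by study day: 5 to 18 is Week 1, 19 to 42 is Week 4, 43 to 70 is Week 8, and 71 to 98 is Week 12. Two exclusions matter here:

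- "Data collected at early termination and unscheduled visits prior to study day 5 will not be analyzed", apart from baseline values.
- Where "no analyses are planned for the assessment at the mapped visit, the data collected at the early termination or unscheduled visit will not be included".

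The planned displays are:

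- Labs (SAP 7.9.8.3): "Laboratory test results will be summarized descriptively at Baseline and Week 12", and "shifts from Baseline to Week 12 in laboratory test results based on normal ranges will be summarized". No other post-dose time point is named.
- ECG shifts (SAP 7.9.8.5.1): "Change from Baseline in ECG abnormalities will be summarized using shift tables at the Week 12 visit".
- ECG descriptive statistics (same section): "Descriptive statistics by treatment group and visit will be provided for the following ECG parameters", with no visits named.
- Treatment-emergent ECG abnormalities (same section): a table without visits, for safety-population subjects with at least one ECG after application.

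SAP 7.9.2 keeps all values in the data listings.

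**The concern.** The ET visit exists partly to obtain a post-dose lab and ECG from subjects who will not reach Week 12. Protocol 10.2 tells sites to try to arrange it promptly when consent is withdrawn. Protocol 10.3 asks for all reasonable efforts to obtain end-of-study procedures when study drug is stopped early. Under SAP 7.9.2 a result from an ET visit before Day 71 is collected and listed, but does not reach the tables that compare lab and ECG shifts between arms.

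The omission falls on early leavers, some of whom leave because of adverse events. They can belong to the safety population (SAP 7.8.3), on which all safety analyses are to be run. Nothing compensates for the loss, since the multiple imputation in SAP 7.3 covers efficacy data only. The Week 12 tables will therefore describe mainly subjects who stayed to about Week 12. No direction of bias is shown, and no efficacy inference is touched.

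**Working it through.** The plan states no figure on this point, so there is none to reproduce. The check maps each study day under SAP 7.9.2 and compares the result with the visits at which analyses are planned.

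**Day mapping.** Window length = last day − first day + 1.

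| ET visit on study day | Assigned to | Days | Lab summary or shift planned? | ECG shift planned? |
|---|---|---|---|---|
| 1–4 | not analyzed | 4 | no | no |
| 5–18 | Week 1 | 14 | no | no |
| 19–42 | Week 4 | 24 | no | no |
| 43–70 | Week 8 | 28 | no | no |
| 71–98 | Week 12 | 28 | yes | yes |

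The windows are contiguous and do not overlap. Day 70 maps to Week 8 and Day 71 is the first day that maps to Week 12. No day before Day 71 can reach a Week 12 table.

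**Share of days.**

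- Treatment period: 12 × 7 = 84 days. Days that cannot reach the Week 12 tables: 4 + 14 + 24 + 28 = 70. 70/84 = 83.3%.
- Windowed days: 14 + 24 + 28 + 28 = 94. Windowed days outside Week 12: 14 + 24 + 28 = 66. 66/94 = 70.2%.

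These are shares of days, not of subjects.

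**Per subject.** A subject whose ET visit falls on one of the 70 days contributes 0 of 1 scheduled post-dose results to the lab tables, and 0 of 1 to the ECG shift table.

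**Number of subjects.** The documents give no dropout rate or timing, so this is a unit conversion only. Each 1% of subjects who leave before Day 71 and attend an ET visit is 700 × 0.01 = 7 subjects: 467 × 0.01 = 4.67 active and 233 × 0.01 = 2.33 vehicle. An assumed range of 1% to 10% gives 7 to 70 subjects.

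**Does another clause restore the values?** SAP 7.9 says "All data collected at scheduled time points will be summarized, regardless of treatment with study drug", and adds that post-treatment assessments count for subjects who stop treatment but remain in follow-up. That covers scheduled visits of subjects still in the study. A subject who exits through an ET visit falls under the specific rule in 7.9.2. Extra labs drawn at unscheduled visits follow the same mapping and exclusion.

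**Tables without visits.** SAP 7.9.2 excludes values from analyses without saying that it means by-visit analyses only. It is therefore unclear whether the exclusions also apply to the worst post-baseline local skin reaction (LSR) grade (SAP 7.9.8.4) and to treatment-emergent ECG abnormalities (SAP 7.9.8.5.1). Read literally they would, and a subject could then count in the ECG denominator while the abnormal value itself is excluded. The LSR exposure is narrow: severe scores, and reactions between visits, are recorded as adverse events (Protocol 9.4.5), and ET scores in a window without scheduled data are kept.

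**The case against.** The rule is explicit, pre-specified and blind to arm, and it sensibly keeps an early value out of a table labelled Week 12. No passage is contradicted and no figure is wrong. Much is also covered elsewhere. All values are listed. Clinically significant labs must be recorded as adverse events (Protocol 9.4.4, 9.4.6.1 and 11.13). Reasons for discontinuation and adverse events leading to it are summarized (SAP 7.9.3 and 7.9.8.2). The ECG case is weaker than the lab case, because the treatment-emergent abnormality table names no visit and on its natural reading would include an early ET ECG. Shares of days say nothing about how many subjects are affected. Protocol 10.3 concerns stopping study drug, and those who stop but stay in the study do reach the Week 12 tables.

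Most of this stands as a limit on the point's weight. A subject withdrawn for a lab abnormality would ordinarily be visible among the adverse events or discontinuation reasons. Protocol 10.2 is the closer reference for subjects who withdraw consent.

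What the objection does not answer is the gap below the threshold of clinical significance. A shift table on normal ranges is meant to show between-arm movement that individual investigators did not report, and listings do not summarize it. For ECGs the adverse event route is less explicit: Protocol 9.4.6.1 names laboratory values and vital signs, and Protocol 9.4.3 gives no reporting rule for ECG values, so only the general definition in Protocol 9.4.6 applies.

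**Conclusion.** The point holds and is minor. An ET lab before Day 71 enters no lab summary or shift table, and an ET ECG before Day 71 does not enter the ECG shift table. ET values from Days 71 to 98 are kept when no scheduled Week 12 value exists. For ECGs the loss is certain only for the shift table, since an early value may still appear in the by-visit descriptive statistics or the treatment-emergent table.

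The conclusion rests on the text of SAP 7.9.2, 7.9.8.3 and 7.9.8.5.1 and on no assumption about dropout. What is lost is the between-arm shift display of values not reported as adverse events, in an unknown number of subjects who leave early. The uncertainty about tables without visits is a secondary request for clarification; the conclusion does not depend on it.

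**What to change.** Before unblinding, amend the SAP as follows.

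1. Keep the Week 12 lab and ECG tables unchanged.
2. Add an end-of-study lab and ECG change and shift table using each subject's last value after the first dose from the Week 12 or ET visit, whatever the study day. Say whether unscheduled repeats count. Label the table as pooling different exposure durations and different times since the last application.
3. State in 7.9.2 that the mapping and exclusions apply only to by-visit summaries.
4. State that worst post-baseline LSR grade and treatment-emergent ECG abnormalities use all assessments after the first dose, including ET and unscheduled visits.

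The cost is a few sentences and one extra set of tables from data already collected and listed. The drawback is that end-of-study values mix exposure durations, which is why the Week 12 tables should stay.
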